Appendix D
Guidelines for Evaluation of Objective Tumour Response Using RECIST
1.1 (Response Evaluation Criteria in Solid Tumours)

1. INTRODUCTION

This appendix details the implementation of RECIST (Response Evaluation Criteria in Solid Tumours) 1.1 guidelines ([Eisenhauer et al 2009](#)) for the study with regards to investigator assessment of tumour burden including protocol-specific requirements for this study.

2. DEFINITION OF MEASURABLE, NON-MEASURABLE, TARGET AND NON-TARGET LESIONS

Patients with at least one lesion measurable that can be accurately assessed at baseline by computerised tomography (CT), magnetic resonance imaging (MRI) or plain X-ray should be included in this study.

Measurable lesions

At least one lesion, not previously irradiated, that can be accurately measured and not chosen for biopsy during the study screening period, at baseline as ≥ 10 mm in the longest diameter (except lymph nodes which must have short axis ≥ 15 mm) with computered tomograpghy (CT) or magnetic resonance imaging (MRI) which is suitable for accurate repeated measurements.

Non-measurable lesions

- All other lesions, including small lesions (longest diameter < 10 mm or pathological lymph nodes with ≥ 10 mm to < 15 mm short axis at baseline. Nodes with < 10 mm short axis are considered non-pathological and should not be recorded as non-target lesions (NTLs)
- Truly non-measurable lesions include the following: bone lesions, leptomeningeal disease, ascites, pleural / pericardial effusion, inflammatory breast disease, lymphangitic involvement of skin or lung, abdominal masses/abdominal organomegaly identified by physical examination that are not measurable by CT or MRI
- Previously irradiated lesions as localised post-radiation changes, which affect lesion sizes, may occur. Therefore, lesions that have been previously irradiated will not be considered measurable and should be selected as NTLs at baseline and followed up as part of the NTL assessment
- Lesions chosen for biopsy during the study screening period if still present should be selected as NTL at baseline and follow up as part of the NTL assessment
- Skin lesions assessed by clinical examination
- Brain metastasis

Special cases

- Lytic bone lesions or mixed lytic–blastic lesions, with identifiable soft tissue components, can be considered measurable if the soft tissue component meets the definition of measurability. Blastic lesions are considered non-measurable.
- Cystic metastases can be considered measurable lesions if they meet the criteria for measurability from a radiological point of view, but if non-cystic lesions are present in the same patient, these non-cystic lesions should be selected as the target lesions (TLs).

Target lesions

A maximum of 5 measurable lesions (with a maximum of 2 lesions per organ), representative of all lesions involved suitable for accurate repeated measurement, should be identified as TLs at baseline.

Non-target lesions

All other lesions (or sites of disease) not recorded as TLs should be identified as NTLs at baseline.

3. METHODS OF MEASUREMENT

The same method of assessment and the same technique should be used to characterise each identified and reported lesion at baseline and during follow-up.

The methods to be used for RECIST assessment are summarised in [Table 1](#) and those excluded for tumour assessments in this study are discussed below, with the rationale provided.

Table 1 Summary of Methods of Assessment

Target Lesions	Non target lesions	New Lesions
CT (preferred)	CT (preferred)	CT (preferred)
MRI	MRI	MRI
	Clinical examination	Clinical examination
	X-ray, chest X-ray	X-ray, chest X-ray
		Ultrasound
		Bone scan
		FDG-PET

3.1 CT and MRI

CT and MRI are generally considered to be the best currently available and reproducible methods to measure TLs selected for response assessment and to assess NTLs and identification of new lesions.

In this study it is recommended that CT examinations of the chest and abdomen will be used to assess tumour burden at baseline and follow-up visits. CT examination with intravenous contrast media administration is the preferred method. MRI should be used where CT is not feasible or it is medically contra-indicated. For assessment of brain lesions MRI is the preferred method.

3.2 Clinical examination

Clinical examination will not be used for assessment of TLs. Clinically detected lesions can be selected as TLs if they are then assessed by CT or MRI scans. Clinical examination can be used to assess NTLs in patients that also have other lesions assessable by CT, MRI or plain Xray and to identify the presence of new lesions.

3.3 X-rays

3.3.1 Plain X-ray

Plain X-rays may be used as a method of assessment for bone NTLs and to identify the presence of new bone lesions.

3.3.2 Chest X-ray

Chest X-rays will not be used for assessment of TLs as they will be assessed by CT or MRI examination. Chest X-rays can, however, be used to assess NTLs and to identify the presence of new lesions.

3.4 Ultrasound

Ultrasound examination will not be used for assessment of TLs and NTLs as it is not a reproducible method, does not provide an accurate assessment of tumour size and it is subjective and operator dependent. Ultrasound examination can, however, be used to identify the presence of new lesions. If new clinical symptoms occur and an ultrasound is performed then new lesions should be confirmed by CT or MRI examination.

3.5 Endoscopy and laparoscopy

Endoscopy and laparoscopy will not be used for tumour assessments as they are not validated in the context of tumour measurements.

3.6 Tumour markers

Tumour markers will not be used for tumour response assessments per RECIST 1.1.

3.7 Cytology and histology

Histology will not be used as part of the tumour response assessment per RECIST 1.1.

Cytological confirmation of the neoplastic origin of any effusion that appears or worsens during treatment is required when the measurable tumour has met criteria for response or stable disease. In such circumstances, the cytology is necessary to differentiate between response / stable disease (an effusion may be a side effect of the treatment) and progressive disease (if the neoplastic origin of the fluid is confirmed). Where cytology findings are not available, any effusion that significantly worsens (from trace to large) or the appearance of a clinically significant effusion (requiring change in drug therapy) during the study treatment will be considered to be progression of NTLs or disease progression due to new lesions.

3.8 Isotopic bone scan

Bone lesions identified on an isotopic bone scan at baseline and confirmed by CT, MRI or X-ray at baseline should be recorded as NTLs and followed by the same method as per baseline assessment.

Isotopic bone scans may be used as a method of assessment to identify the presence of new bone lesions at follow-up visits. New lesions will be recorded where a positive hot-spot that was not present on the baseline bone scan assessment is identified on a bone scan performed at any time during the study. The Investigator should consider the positive hot-spot to be a significant new site of malignant disease and represent true disease progression in order to record the new lesion. Confirmation by CT, MRI and x-ray is recommended where bone scan findings are equivocal.

3.9 FDG-PET scan

FDG-PET (fluorodeoxyglucose positron emission tomography) scans may be used as a method for identifying new lesions, according with the following algorithm: New lesions will be recorded where there is positive FDG uptake (defined as when an uptake greater than twice that of the surrounding tissue is observed) not present on baseline FDG-PET scan or in a location corresponding to a new lesion on CT/MRI at the same follow-up visit. If there is no baseline FDG-PET scan available, and no evidence of new lesions on CT/MRI scans then follow-up CT/MRI assessments should be continued, scheduled as per protocol or clinical indicated, in order to confirm new lesions.

4. TUMOUR RESPONSE EVALUATION

4.1 Schedule of evaluation

CT examinations of the chest and abdomen (including liver adrenal glands) will be used to assess tumour burden at baseline and follow-up visits. CT examination with intravenous contract media administration is the preferred method. MRI should be used where CT is no feasible or it is medically contra-indicated.

Baseline tumour assessments should encompass all areas of known predilection for metastases in the disease under evaluation and should additionally investigate areas that may be involved based on signs and symptoms of individual patients and should be performed no more than 28 days before the start of study treatment. CT/MRI scan of the brain should be performed in patients with known or suspected brain metastases. Follow-up assessments should be performed every 6 weeks (± 7 days) after the start of treatment until discontinuation of study treatment or withdrawal of consent. Any other sites at which new disease is suspected should also be adequately imaged at follow-up.

If an unscheduled assessment was performed and the patient has not progressed, every attempt should be made to perform the subsequent assessments as their scheduled visits. This schedule is to be followed in order to minimise any unintentional bias caused by some patients being assessed at different frequency than other patients.

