(a) A total of 175 patients will be treated with AZD9291. Patient enrolment will consist of 2 cohorts: approximately 50 patients with T790M+ NSCLC who have progressed following EGFR-TKI treatment but who have not received further treatment, and approximately 125 patients with T790M- NSCLC who have progressed following minimum prior therapy with an EGFR-TKI and a platinum-based doublet chemotherapy. Patients may have also have received additional lines of treatment.

(b) Patients will be considered enrolled at the time AZD9291 treatment is started. Patients will continue to receive AZD9291 treatment until objective disease progression (according to RECIST 1.1) or for as long as they are receiving clinical benefit in the opinion of the Investigator. Patients who discontinue study treatment for reasons other than disease progression must continue tumour assessments as per the protocol schedule until progression.

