3.7 Withdrawal from the study

The term withdrawal from the study refers to both discontinuation from study treatment and study assessments.

Patients may be withdrawn from the study for the following reasons:

- Screen failure
- Death
- Withdrawal of consent

If a patient wishes to withdraw their consent to both treatment and study assessments, they should be asked if they are willing to continue with survival follow-up (which can be conducted by telephone – see [Section 4.3.4](#)). If a patient wishes to withdraw their consent to further participation in the study entirely, including survival follow-up this should be clearly documented in the patient notes and in the clinical study database.

Withdrawn patients will not be replaced.

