4.3.3 Progression follow-up

Patients who discontinue AZD9291 for reasons other than progression will continue RECIST 1.1 assessments every 6 weeks (relative to first dose of AZD9291) for objective progression. In addition to RECIST 1.1 assessments, the following assessments are also required during this follow-up period as detailed in the Study Plan (see [Table 1](#)):

- EORTC QLQ-C30 and EQ-5D-5L every 6 weeks and at the time of progression.
- EORTC QLQ LC13 and PRO-CTCAE every 3 weeks and at the time of progression.
- Plasma for ctDNA collected every 6 weeks up to and including progression (corresponding with the RECIST assessments – and continuing after treatment discontinuation if this is in absence of progression)
- Adverse event collection detailed in [Table 8](#)
- Anti-cancer therapy collected every 6 weeks.

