5.1 Efficacy assessments

5.1.1 RECIST 1.1

All imaging assessments including unscheduled visit scans should be collected on an ongoing basis and sent to an AstraZeneca (AZ) appointed Clinical Research Organisation (CRO) to enable independent central analyses.

For both Independent Central Review (ICR) and investigator review RECIST 1.1 criteria will be used to assess each patient's tumour response to treatment and allow calculation of ORR, PFS, DCR, DoR, and assess tumour shrinkage. The RECIST 1.1 guidelines for measurable, non-measurable, target and non-target lesions and the objective tumour response criteria [CR (complete response), PR (partial response), SD (stable disease) or PD (progression of disease)] are presented in [Appendix D](#). For ORR, a visit response of CR or PR must be confirmed by a later scan conducted at least 4 weeks after the initial response is observed. See [Section 4](#) for considerations related to RECIST 1.1 assessments.

The methods used at baseline for assessment of tumour burden [CT or MRI scans of chest and abdomen (including liver and adrenal glands)] must be used at each subsequent follow-up assessment. Any other areas of disease involvement should be additionally investigated based on the signs and symptoms of individual patients. CT/MRI scan of the brain should be performed in patients with known or suspected brain metastases. The baseline assessment should be performed within 28 days of treatment start. Assessments to be performed every 6 weeks relative to first dose until objective disease progression. It is important to follow the assessment schedule as closely as possible. If scans are performed outside of the scheduled visit \pm 1 week window interval and the patient has not progressed, every attempt should be

made to perform the subsequent scans at their scheduled time points. Any other sites at which new disease is suspected should also be appropriately imaged.

If the investigator is in doubt as to whether progression has occurred, particularly with response to non-target lesions (NTLs) or the appearance of a new lesion, it is advisable to continue treatment until the next scheduled assessment or sooner if clinically indicated and reassess the patient's status. If repeat scans confirm progression, then the date of the initial scan should be declared as the date of progression.

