6.7 Management of IP related toxicities

If a patient experiences a CTCAE grade 3 or higher and/or unacceptable toxicity (any grade) not attributable to the disease or disease-related processes under investigation, where the Investigator considers the AE of concern to be specifically associated with AZD9291, dosing will be interrupted and supportive therapy administered as required in accordance with local practice/guidelines.

If the toxicity resolves or reverts to \leq CTCAE grade 2 within 3 weeks of onset, treatment with AZD9291 may be restarted at the same dose (80 mg) or a lower dose (40 mg) using the rules below for dose modifications (Table 9) and with discussion and agreement with the AstraZeneca Study Team Physician as needed. There will be no individual modifications to dosing schedule in response to toxicity, only potential dose reduction or dose interruption.

If the toxicity does not resolve to \leq CTCAE grade 2 after 3 weeks, then the patient should be withdrawn from the study and observed until resolution of the toxicity.

Table 9 Dose interventions

Intervention	AZD9291 Dose
Starting Dose	80 mg

Table 9 **Dose interventions**

Intervention	AZD9291 Dose
Reduced Dose –1	40 mg

On resolution of toxicity within 3 weeks:

- If an AE subsequently requires dose interruption, AZD9291 may restart at the same dose or the reduced dose, on resolution/improvement of the AE at the discretion of the Investigator.

If new or worsening pulmonary symptoms (eg, dyspnoea) or radiological abnormality suggestive of interstitial lung disease is observed, an interruption in study treatment dosing is recommended, and the AstraZeneca study team should be informed. A questionnaire regarding the results of the full diagnostic workup (including high-resolution computed tomography (HRCT), blood and sputum culture, haematological parameters) will be sent to Investigators. It is strongly recommended to perform a full diagnostic workup, to exclude alternative causes such as lymphangitic carcinomatosis, infection, allergy, cardiogenic edema, or pulmonary hemorrhage. In the presence of confirmatory HRCT scans where other causes of respiratory symptoms have been excluded, a diagnosis of interstitial lung disease should be considered and study treatment permanently discontinued.

In the absence of a diagnosis of interstitial lung disease study treatment may be restarted following consultation with the AstraZeneca Study Team Physician.

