4.5 Symptomatic deterioration

Symptomatic deterioration is not a descriptor of an objective response: it is a reason for stopping study therapy.

Patients with ‘symptomatic deterioration’ requiring discontinuation of study treatment without objective evidence of disease progression at that time should continue to undergo RECIST 1.1 assessments according to the clinical study protocol until objective disease progression is observed.

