3.6.1 Procedures for discontinuation of a subject from investigational product

Previous text:

Any subject who discontinues study treatment for reasons other than objective disease progression should have tumour assessments performed as scheduled in the protocol (See Table 1) until objective disease progression is documented or death occurs, unless consent is withdrawn. Study procedures related to PROs, SAEs and anti-cancer treatment must be captured until the subject no longer has RECIST 1.1 assessments (disease progression or permanent withdrawal from the study).

Revised text:

Any subject who discontinues study treatment for reasons other than objective disease progression should have tumour assessments performed as scheduled in the protocol (See Table 1) until objective disease progression is documented or death occurs, unless consent is withdrawn. ~~Study procedures related to PROs, SAEs and anti-cancer treatment must be captured until the subject no longer has RECIST 1.1 assessments (disease progression or permanent withdrawal from the study).~~ **Refer to Section 4.3 for further details.**

Section of protocol affected:

Table 1 Study Plan

Previous text:

Footnote r Following AZD9291 discontinuation, SAEs considered related to study procedures should continue to be collected until disease progression.

Revised text:

Footnote r Following AZD9291 discontinuation, SAEs considered related to study procedures should continue to be collected **as outlined in Table 8.**

Time relative to dose	Screening (baseline)	Cycle 1 Day 1	Cycle 2 Day 1	Cycle 3 Day 1
24 hours (±1 hour)	X			X (D2, pre-dose)

1 Since there is no dosing at Screening, ECG recordings should start at a time that would be consistent with planned dosing times at Cycle 1 Day 1, Cycle 2 Day 1 and Cycle 3 Day 1 (for baseline purposes).

Revised text:

Time relative to dose	Screening (baseline)	Cycle 1 Day 1	Cycle 2 Day 1	Cycle 3 Day 1
Pre-dose (-10 to 0 min) ²	X ¹	X	X	X
1 hour (±5 min)	X	X		X
2 hours (±10 min)	X	X		X
4 hours (±10 min)	X	X		X
6 hours (±10 min)	X	X		X
8 hours (±10 min)	X	X		X
10 hours (±10 min)	X			X
12 hours (±1 hour)	X			X
24 hours (±1 hour)	X			X (D2, pre-dose)

1 Since there is no dosing at Screening, ECG recordings should start at a time that would be consistent with planned dosing times at Cycle 1 Day 1, Cycle 2 Day 1 and Cycle 3 Day 1 (for baseline purposes).

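### Appendix D 4.1 ends tumour scans when treatment stops, and Section 6.7 withdraws some toxicity patients from the study; both conflict with the protocol's rule to scan until progression and must be reconciled

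*Supplement*

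**What the plan says.** **Scan duration.** Appendix D 4.1 gives the schedule as every 6 weeks "after the start of treatment until discontinuation of study treatment or withdrawal of consent". The other passages set a different end:

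- Section 1.5, note (b) to Figure 1: patients who stop for reasons other than progression "must continue tumour assessments as per the protocol schedule until progression".
- Section 3.6.1, where Amendment 2 keeps the scan rule: scans continue "until objective disease progression is documented or death occurs, unless consent is withdrawn".
- Section 4.3.3: "Patients who discontinue AZD9291 for reasons other than progression will continue RECIST 1.1 assessments every 6 weeks".
- Section 5.1.1: "Assessments to be performed every 6 weeks relative to first dose until objective disease progression".
- Table 1: the tumour assessment row runs to disease progression.
- Appendix D 4.5: patients who stop for symptomatic deterioration "should continue to undergo RECIST 1.1 assessments according to the clinical study protocol until objective disease progression is observed".

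**Withdrawal after toxicity.** For toxicity that has not come down to grade 2 or less after 3 weeks, Section 6.7 says "then the patient should be withdrawn from the study and observed until resolution of the toxicity". Section 3.7 defines the term: "The term withdrawal from the study refers to both discontinuation from study treatment and study assessments". Its listed reasons are screen failure, death and withdrawal of consent; toxicity is not among them. The QTcF paragraph of Section 6.7 ends study treatment only.

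**The concern.** Section 8.4, as amended, counts PFS events whether or not the patient has left study therapy, so the analysis needs scans after treatment stops. Appendix D 4.1, read literally, does not supply them for any patient who stops without progression. Section 6.7, read with the definition in Section 3.7, does not supply them for patients with unresolved toxicity.

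Three endpoints depend on those scans. A patient without a PFS event is censored at the last evaluable RECIST assessment, and so is one who progresses or dies after three or more missed assessments. DoR takes over the PFS censoring time. ORR, the primary endpoint, counts only responses confirmed at least 4 weeks later, and the primary cut-off is timed to allow two follow-up scans for every patient. If a patient responds at week 6 and both drug and scans stop before week 12, the scheduled confirming scan is missing. Scans that were not done cannot be recovered at analysis.

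**Working it through.** **1. Do the passages really conflict?** For a patient who stops AZD9291 without progression and without withdrawing consent:

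| Passage | Are scans continued? |
|---|---|
| Figure 1 note (b), 3.6.1, 4.3.3 | Yes, stated for this case |
| 5.1.1, Table 1 | Yes, to progression |
| Appendix D 4.5 | Yes, after symptomatic deterioration |
| Appendix D 4.1 | No |
| 6.7 read with 3.7 (toxicity unresolved after 3 weeks) | No |
| 6.7, QTcF paragraph | Treatment ends; nothing said about scans |

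Appendix D 4.1 also differs in the other direction. Section 4.2 drops study RECIST scans for patients treated beyond progression, while Appendix D 4.1 would continue them until the drug stops. Neither amendment touches Appendix D 4.1 or the withdrawal sentence in Section 6.7, so both conflicts stand in the current text.

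**2. Possible size for PFS.** The plan states no figure to reproduce, and every rate here is an assumption. On-treatment PFS is exponential with median 9 months, so λ = ln 2 / 9 = 0.0770 per month. A fraction d = 7-15% of patients is given a stop time uniform over 0-9 months; about 5-11% of all patients then stop before progressing. After stopping, the median time to progression is 4 or 2 months, so the hazard ratio is h = 9/4 = 2.25 or 9/2 = 4.5.

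With full follow-up and t ≤ 9, S(t) is the sum of two parts:

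- on treatment: e^(−λt) × (1 − d·t/9)
- stopped: (d/9) × e^(−hλt) × (e^((h−1)λt) − 1) / ((h−1)λ)

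Check for d = 0.07, h = 2.25, t = 8.71: 0.4766 + 0.0234 = 0.500, so the true median is 8.71 months. For d = 0.15, h = 4.5 it is 7.95 months.

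If every stopping patient is censored at the stop, Kaplan-Meier estimates the on-treatment curve, whose median is 9.00. The overstatement is 9.00 − 8.71 = 0.29 month up to 9.00 − 7.95 = 1.05 months. At 12 months the estimate is 39.7% against a true 38.3% to 34.7%, which is 1.4 to 5.0 points too high.

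If only a fraction a of stopping patients loses scans, the observed hazard is λ(on + h(1−a)·off) / (on + (1−a)·off), where on and off are the two parts above:

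| Share affected (a) | Median overstated by | 12-month PFS overstated by |
|---|---|---|
| 100% | 0.29 to 1.05 months | 1.4 to 5.0 points |
| 20% | 0.05 to 0.17 month | 0.3 to 0.9 point |
| 10% | 0.03 to 0.09 month | 0.1 to 0.5 point |

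With h = 1 the observed hazard equals λ for any a, so the bias is zero.

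**3. Possible size for ORR.** Take 70 of 175 responders, the 40% used as an example in Section 8.2; the exact (Clopper-Pearson) interval is 32.7-47.7%. Suppose about 2%, 5% or 10% of responders lose their confirming scan:

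- 69/175 = 39.4% (32.1-47.1)
- 66/175 = 37.7% (30.5-45.3)
- 63/175 = 36.0% (28.9-43.6)

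This error runs downward, opposite to the possible error in PFS and DoR.

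**The case against.** The main rule is stated often and clearly, in the body, in Table 1 and once in Appendix D itself. Table 7 and Table 8 provide for a period after discontinuation and before progression, and Amendment 2 added a pointer from Section 3.6.1 to Section 4.3. Section 5.1.1 sends the reader to Appendix D for lesion definitions and response criteria and gives the schedule itself. Most sites may therefore never act on the conflicting clause. That argument stands as to likelihood. It does not remove the conflict: Appendix D says it carries protocol-specific requirements, 4.1 says its schedule is to be followed, and the documents contain no rule that the body prevails over an appendix.

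A reader might infer several stronger things that the documents do not support:

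- *That PFS and DoR will be biased upward.* This needs sites to follow the minority wording and the progression risk to rise after stopping. The documents quantify neither. Deaths after fewer than three missed assessments still count as PFS events, which softens any bias.
- *That all toxicity patients lose follow-up.* The Section 6.7 sentence covers only toxicity not at grade 2 or less after 3 weeks. The interstitial lung disease and QTcF rules speak of treatment only.
- *That a week-6 response could never be confirmed.* Unscheduled scans go to central review, and a suitable scan at least 4 weeks later can confirm.
- *That this is a design choice.* The design is to scan until progression; two sentences fail to say so.

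It is also fair that PFS and DoR are secondary and descriptive in a single-arm estimation study, and that lost confirmations err on the conservative side for ORR.

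**Conclusion.** The point holds as an internal inconsistency that is wrong as written. Its effect is conditional: at sites that follow Appendix D 4.1 or the Section 6.7 sentence literally, scans after treatment stops could be lost. The overstatement of median PFS ranges from zero (unchanged hazard) through under 0.2 month (20% of stopping patients affected) to about 0.3 to 1.0 month (every site following Appendix D 4.1). The non-zero figures rest on assumed stop rates of 7-15%, a 9-month median and a 2.25 to 4.5-fold rise in hazard, none of which the documents give. DoR shares the PFS censoring and so the direction of the error. Unconfirmed responses would lower ORR, by 0.6 to 4.0 points if about 2-10% of responders were affected. The correction is cheap and protects data that cannot be rebuilt later, so it should be made even though the harm may be small.

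**What to change.** In Appendix D 4.1, replace the end of the scan schedule with the one already in Sections 3.6.1 and 4.3.3: until objective progression or death, unless consent is withdrawn.

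In Section 6.7, reconcile the two withdrawal wordings (unresolved toxicity and QTcF) with Sections 3.7 and 4.3.3, so that a site can tell whether outcome assessments continue. The clinical stopping rule itself is not in question.

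The cost is two sentences in an amendment and a letter to sites. The Appendix D change adds no procedure beyond those Section 4.3.3 already requires.
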